## 5 STUDY ENROLLMENT AND WITHDRAWAL

## 5.1 PARTICIPANT INCLUSION CRITERIA

Individuals must meet all of the inclusion criteria set forth below in order to qualify for inclusion in this study.

- Adults, 18 years of age or older at the time of implantation
- Conductive or mixed hearing loss, defined as:
  - Conductive hearing loss with pure-tone average (PTA) for bone conduction thresholds better than or equal to 25 dB at 500, 1000, 2000 and 3000 Hz
  - Mixed hearing loss with PTA for bone conduction thresholds better than or equal to 45 dB at 500, 1000, 2000, and 3000 Hz
- Sufficient air-bone gap at 500, 1000, 2000, and 3000 Hz to demonstrate potential for improvement
- Ability to benefit from amplification as defined by an unaided word recognition score of 30% correct or better
- Bilateral BONEBRIDGE can be considered if the difference in PTA for bone conduction thresholds is 10 dB or less between the right and left ears
- Prior experience with acoustic or bone conduction hearing aids, unless candidate is unable to wear amplification for medical reasons
- Able to complete testing materials in English
- CT scan indicating the patient's anatomy is adequate to enable placement of the implant
- Ability to undergo general anesthesia
- Appropriate motivation and expectation levels
- Stated willingness to comply with all study procedures for the duration of the study

[figure not shown]

FIGURE 1 – Example inclusion audiogram showing audiometric threshold criteria.

NOTE: Subjects may fall outside of the shaded area but still meet the PTA criteria.

## 5.2 PARTICIPANT EXCLUSION CRITERIA

Any individual meeting the below exclusion criteria at the candidacy evaluation will be excluded from study participation.

- Evidence that hearing loss is retrocochlear in origin
- Skin or scalp condition precluding use of external audio processor
- Suspected cognitive impairment or organic brain dysfunction

#### 5.3 STRATEGIES FOR RECRUITMENT AND RETENTION

Participants in the study will be enrolled at the three clinical trial sites involved. Each site should aim to recruit 10 subjects in order to reach the sample size of 30 subjects. Two investigative sites from within the United States will be included; one site will be located in Canada. Sites should recruit candidates with both conductive and mixed hearing loss, with the intention of enrolling 15 subjects with mixed hearing loss and 15 subjects with conductive hearing loss. If needed, the total number of subjects enrolled may exceed 30 in order to have roughly equal subgroups based on type of hearing loss.

Subject recruitment is expected to take approximately 18 months. Each site should expect to enroll one to two subjects per six-month period throughout the duration of the study. At this rate, we expect to have 30 subjects enrolled in the trial within 18 months.

## 5.4 PARTICIPANT WITHDRAWAL OR TERMINATION

## 5.4.1 REASONS FOR WITHDRAWAL OR TERMINATION

Subjects may voluntarily withdraw from the study at any point. Subjects who choose to withdraw or are terminated from the study should be reported to study monitors as soon as possible. Subjects who are considered lost-to-follow-up should also be reported to study monitors immediately.

## 5.4.2 HANDLING OF PARTICIPANT WITHDRAWALS OR TERMINATION

Withdrawn subjects will continue to be seen by their clinical audiologist and surgeon for regular follow-ups, but no additional data will be collected. Subjects may voluntarily withdraw from the study at any time without fear of repercussion or loss of benefit from the study device. When withdrawing, the subject should contact study personnel at their implanting site, who will contact the study monitor. Reasons for withdrawal will be described in study reports.

Page 9 of 26

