## 4 STUDY DESIGN AND ENDPOINTS

## 4.1 DESCRIPTION OF THE STUDY DESIGN

Approximately 30 subjects will be enrolled across three centers in this single-arm, repeated measures study, where each subject serves as his or her own control. Of the 30 subjects recruited into the study, 15 subjects with mixed hearing loss and 15 subjects with conductive hearing loss will be recruited across all three sites. After enrollment/baseline assessment confirms candidacy, qualified individuals will receive a BONEBRIDGE Bone Conduction Implant. Each subject will subsequently be fit with a SAMBA Audio Processor.

Activation will occur at two weeks post-implantation. Follow-up evaluations will occur at two weeks, one month, and three months post-activation. Soundfield thresholds, as well as speech perception testing in quiet and in noise, will be measured at the follow-up intervals. Results will be compared to the pre-operative unaided condition. In addition to any complications reported on a surgical questionnaire, safety outcomes will be collected and reported as the number and proportion of subjects experiencing a known risk. The three-month interval will be considered the primary safety and effectiveness endpoint.

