## 4.2 STUDY ENDPOINTS

## 4.2.1 PRIMARY ENDPOINTS

Primary endpoints are as follows:

- 1. Comparison of AzBio sentence score in noise with the BONEBRIDGE at three months post-activation to the pre-operative unaided score. Testing will be completed in the soundfield at 60 dB SPL with a +5 dB signal-to-noise ratio (SNR). Improvement will be defined as equal to or greater than 10 percentage points.
- 2. Number and proportion of subjects experiencing known risks, as listed above in Section 2.2.1.

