## 8.2 TIME PERIOD AND FREQUENCY FOR EVENT ASSESSMENT AND FOLLOW-UP

The occurrence of an event may be brought to the attention of the investigator during study visits, interim visits, or phone conferences over the duration of the study. All events will be reported on the Risk Occurrence case report form. Information to be collected on the CRF includes: event description, date of onset, time of onset, seriousness, and the date/time of resolution (if applicable).

Investigators should record all reportable events with start dates occurring any time after the IC is obtained. Any medical condition that is present at the enrollment/baseline evaluation will not be reported as an event. If the subject's condition deteriorates at any time during the study, however, the event will be reported.

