## 10.2.2 ANALYSIS OF THE PRIMARY ENDPOINTS

The mean change in AzBio sentence score from baseline to 3 months post-activation will be summarized as a continuous variable using the descriptive statistics described in section 10.4.1. Additionally, a one-sided, paired t-test comparing the mean change in AzBio sentence score to the superiority margin of 10 will be performed and the corresponding p-value will be reported. A p-value less than 0.025 will result in rejection of the null hypothesis indicating that the mean change in AzBio sentence score was greater than 10 percentage points.

The rate of occurrence of known risks will be summarized and reported as the number and proportion of subjects experiencing an event.

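### Section 5.4.2 ends all data collection at withdrawal with no exception for safety and conflicts with section 8.2, so the primary safety proportion may be understated

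*Combined protocol and SAP*

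**What the plan says.** All references are to the combined protocol and SAP.

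- **Data after withdrawal (5.4.2).** "Withdrawn subjects will continue to be seen by their clinical audiologist and surgeon for regular follow-ups, but no additional data will be collected". No exception is made for safety. The rule does not separate a subject who refuses any further use of data from one who only stops study testing. The same section has reasons for withdrawal described in study reports.
- **Who is covered (5.4.1 and 5.4.2).** Section 5.4.1 deals jointly with "Subjects who choose to withdraw or are terminated from the study", and withdrawal is allowed at any point. The heading of 5.4.2 covers termination too, but its sentence on data names only withdrawn subjects.
- **Primary safety endpoint (4.2.1 and 4.1).** The second primary endpoint is "Number and proportion of subjects experiencing known risks, as listed above in Section 2.2.1". On timing, section 4.1 says "The three-month interval will be considered the primary safety and effectiveness endpoint".
- **Safety analysis (10.2.2).** "The rate of occurrence of known risks will be summarized and reported as the number and proportion of subjects experiencing an event". There is no test, margin or interval, no stated denominator and no rule for partly followed subjects.
- **Event recording (8.2).** "Investigators should record all reportable events with start dates occurring any time after the IC is obtained". On how events become known: "The occurrence of an event may be brought to the attention of the investigator during study visits, interim visits, or phone conferences". No end of recording at withdrawal is stated.
- **Missing data (10.2.4).** Subjects lost or terminated early are tabulated. The only imputation rule is last observation carried forward for AzBio. Few losses are expected, and no figure is given.

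**The concern.** The device is a surgical implant, so a subject who leaves the study after surgery still carries it and can still have an extrusion, an infection or a displacement. The plan itself expects these subjects to keep seeing a surgeon and an audiologist. The information would therefore often exist, yet 5.4.2 tells sites not to collect it. Section 8.2, read alone, tells them to record it. Three sites could resolve this in different ways, and the safety result would then depend partly on which section each site followed.

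At stake is the second primary endpoint. It is purely descriptive, so the reported number and proportion are the whole result. With about 30 subjects, a single missed subject shows.

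**Working it through.** **The plan's own figures.** The plan states no expected event rate, withdrawal rate or precision for safety, so there is no safety figure to reproduce. Its one computed figure is the 94.2% power of the AzBio test in 10.3. It reproduces: n = 30, mean 30 against a margin of 10, SD 30, one-sided 0.025, noncentrality 20/(30/√30) = 3.651 on 29 degrees of freedom, power 94.16%. This point does not affect it.

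**Step 1: the window.** Under 7.1.2, activation is 2 to 4 weeks after surgery and the three-month visit 10 to 14 weeks after activation. The safety window after surgery is therefore 2 + 10 = 12 to 4 + 14 = 18 weeks. Withdrawal at any time after surgery leaves the rest unobserved under 5.4.2.

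**Step 2: who is missed.** The endpoint counts subjects, not events.
- Known-risk event before withdrawal: already in the numerator.
- No known-risk event by three months: correctly absent from it.
- First known-risk event after withdrawal and before three months: missed.
- Withdrawn before surgery: not implanted, and outside this point.

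Only the third group matters for the overall proportion. If each risk is also tabulated separately, a first event of another type after withdrawal is missed in its own row.

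**Step 3: bounds.** Let m be the number of subjects in the third group. With all 30 in the denominator:

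understatement = m/30

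m = 0, 1, 2, 3 gives 0, 3.3, 6.7 and 10.0 points.

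As an example, assume 3 subjects with recorded events and 3 others withdrawn event-free after implantation. The report shows 3/30 = 10.0%. Full follow-up could show:

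| m | Full follow-up | Understatement |
|---|---|---|
| 0 | 3/30 = 10.0% | 0 |
| 1 | 4/30 = 13.3% | 3.3 points |
| 2 | 5/30 = 16.7% | 6.7 points |
| 3 | 6/30 = 20.0% | 10.0 points |

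The last row requires every withdrawn subject to have a first event afterwards.

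**Step 4: expected size under assumed rates.** Let w be the number withdrawn, b the base risk, r the ratio of risk in withdrawn subjects to that base, and f the share of their risk that falls after withdrawal:

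expected understatement = (w/30) × b × r × f

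Take b = 10%, r = 1 to 3 and f = 0.25 to 0.75, all assumptions:
- w = 1: (1/30) × 0.10 × 1 × 0.25 = 0.1 points, up to (1/30) × 0.10 × 3 × 0.75 = 0.75 points.
- w = 3: (3/30) × 0.10 × 1 × 0.25 = 0.25 points, up to (3/30) × 0.10 × 3 × 0.75 = 2.25 points.
- w = 5: (5/30) × 0.10 × 1 × 0.25 = 0.4 points, up to (5/30) × 0.10 × 3 × 0.75 = 3.75 points.

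**Step 5: the denominator.** If the three withdrawn subjects in the example are dropped, the report shows 3/27 = 11.1%. That is above the full-follow-up value when m = 0 (10.0%) and below it when m is 1 or more (13.3% to 20.0%). The direction of the error thus depends on a choice that 10.2.2 does not make.

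**Scale.** The exact 95% interval is 2.1% to 26.5% for 3/30, and 0 to 11.6% for 0/30.

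**The case against.** The strongest reply is that 8.2 already covers the gap. It asks for every reportable event after consent, accepts events learned of at interim visits or by phone, and does not stop at withdrawal. That reading is possible, but 5.4.2 is the specific rule for withdrawn subjects and says the opposite. The conflict stands, and 8.2 does not clearly settle it.

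A second reply is that the effect is small. Few losses are expected, the interval around any proportion from 30 subjects is wide anyway, and no stated decision depends on the safety result. All of this is true, and it limits the weight of the point. It does not justify leaving uncollected, by rule, information on a primary endpoint. Sampling error and a one-directional loss of events are also different things.

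A third reply is that stopping collection respects the right in 11.3.2 to withdraw consent, and that the consent template, which is not in the public text, may deal with later data. The first part stands for subjects who refuse further use of data. The second cannot be checked, and the protocol text would still need to agree with any such wording.

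Some stronger readings are tempting but unsupported:
- **That withdrawn subjects are the ones most likely to have events.** This is plausible, but nothing in the documents links withdrawal to complications. A subject who leaves because of a known-risk event has already been counted.
- **That events will certainly be seen and not counted.** Given 8.2, the documents support only that they may be missed. Nor do they say that the clinicians seen after withdrawal are the study investigators.
- **That terminated subjects are plainly under the same rule.** They come in only through the section heading.
- **That revision surgery would be hidden from the proportion.** Revision is not a listed known risk; 2.2.1 mentions it only as a possible result of serious complications.
- **That a bias of at least 3.3 points is established.** That presumes a missed subject. The range starts at zero.

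The tabulation of early terminations in 10.2.4 shows how many subjects left, but does not recover their later events.

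**Conclusion.** The point holds as a rule that can lose primary safety data and that contradicts another section. If 5.4.2 is followed, the proportion may be understated by 3.3 points for each implanted subject whose first known-risk event falls after withdrawal and within the window. That is 0 to 10 points for an assumed 0 to 3 such subjects with all 30 in the denominator. The 10-point end is a worst case. Under the rates assumed in the working, three withdrawals cost about 0.25 to 2.25 points on average. Neither the number of withdrawals nor the event rate can be fixed from the documents. The point does not touch the AzBio test or its power. It is worth correcting because the remedy is cheap and the safety result is a bare proportion from about 30 subjects.

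**What to change.** 1. Amend 5.4.2 and reconcile it with 8.2. Implanted subjects who stop study testing, or whom the study terminates, are asked for permission to keep recording known-risk events and device status from their routine clinic visits through three months post-activation. Collection stops only for those who refuse. Name terminated subjects in the text, not only in the heading.
2. State in 8.2 that event recording runs to the three-month point for every implanted subject who has not refused.
3. Define the safety denominator in 10.2.2 as all implanted subjects, and report next to the proportion the number without complete safety follow-up. A range from none to all of those still event-free at last contact having a later event would show how much the gap could matter.

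The cost is a few sentences in the protocol and consent form, IRB approval of the amendment, and a few more case report form entries. No visits are added.

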## 6 STUDY DEVICE

The MED-EL BONEBRIDGE Bone Conduction Implant is a commercially marketed device consisting of the Bone Conduction Implant (BCI 601 or BCI 602) and the Audio Processor. The BCI is the implantable part of the BONEBRIDGE and can only be used together with compatible MED-EL external components. The device is an osseo-integrated bone conduction implant system, intended to provide a level of useful sound perception for individuals with conductive and mixed hearing loss. The BCI is surgically implanted into the mastoid bone.

The externally-worn audio processor is attached to the user's head, behind the ear. A magnet in the audio processor is attracted to an opposing magnet within the implant. The audio processor includes two microphones to pick up sound from the environment, sound processing circuitry to modify the output signal to the user's specific requirements, and a digital compression processor. The device is powered by a single standard battery. The BONEBRIDGE system is activated by fitting the audio processor to the patient.

The implanted part of the BONEBRIDGE system consists of the internal coil and the Bone Conduction Floating Mass Transducer (BC-FMT). A signal from the audio processor is transferred across the skin to the internal coil. The internal coil then relays the signal to the BC-FMT. The BC-FMT converts the signal to vibrations, which are interpreted by the user as sound.

## 7 STUDY PROCEDURES AND SCHEDULE

## 7.1 STUDY PROCEDURES

## 7.1.1 STUDY SPECIFIC PROCEDURES

The following procedures will be performed over the duration of the study and will be documented for each subject enrolled in the study.

- Informed Consent (IC): Investigators will review the IC with potential subjects and obtain signature prior to initiating study activities.
- Medical Assessment: Subjects should be evaluated for their ability to undergo surgery. This
  should include a chart review to document prior surgeries and known health conditions, as
  well as ear-related history. All subjects should also undergo a complete otologic exam and
  radiologic assessment, for proof of adequate anatomy to enable placement of the implant.
- Surgery: BONEBRIDGE surgery will be performed once a subject has consented to participating in the study and completed pre-operative assessment.
- Unaided Thresholds: Unaided air conduction thresholds will be measured pre- and postoperatively at 250, 500, 1000, 2000, 3000, 4000, 6000, and 8000 Hz. Bone conduction thresholds will also be measured at 500, 1000, 2000, 3000, and 4000 Hz in order to determine whether hearing loss is conductive or mixed.

- Sentence Testing: AzBio sentences in noise will be administered at 60 dB SPL with a signalto-noise ratio of +5 dB SNR as the primary outcome measure. Sentence testing will occur in the unaided condition pre-operatively and with the BONEBRIDGE post-operatively. One list will be presented per condition.
- Monosyllabic Word Testing: CNC words in quiet will be administered at 60 dB SPL as a secondary outcome measure. Word testing will occur in the unaided condition preoperatively, and with the BONEBRIDGE post-operatively. One list will be presented per condition.
- Soundfield Thresholds: soundfield thresholds will be measured in the implant ear only at 500, 1000, 2000, 3000, and 4000 Hz pre-operatively and post-operatively.
- Signal-to-Noise Ratio Testing: The QuickSIN will be administered at 60 dB SPL preoperatively in the unaided condition and post-operatively with the BONEBRIDGE. This will be reported as a Signal-to-Noise Ratio Loss.
- Subjective Questionnaires: Subjects will complete the SSQ12 questionnaire (Noble, Jensen, Naylor, Bhullar, & Akeroyd, 2013) and HDSS questionnaire (Luetje, et al., 2002) preoperatively and post-operatively.
- BONEBRIDGE Programming: Programming of the audio processor should occur at each interval after device activation.
- Occurrence of Known Risks: occurrence of risks should be monitored throughout the duration of the study and reported as appropriate.

## 7.1.2 STUDY INTERVALS

- Enrollment/baseline
- Surgery (within 4 months of baseline)
- BONEBRIDGE implant activation (2-4 weeks post-operative)
- 2-weeks post-activation (1.5-3 weeks post-activation)
- 1-month post-activation (3-6 weeks post-activation)
- 3-months post-activation (10-14 weeks post-activation)

Testing can occur outside of the provided window with prior approval from MED-EL.

## 7.2 STUDY SCHEDULE

## 7.2.1 ENROLLMENT/BASELINE

Prior to completing any candidacy or baseline testing, subjects will sign an informed consent (IC) form.

All testing should occur in a sound-treated booth under insert earphones or in the soundfield with the subject seated one meter from the speaker, depending on the test condition. Speaker output should be calibrated prior to conducting study-related testing to ensure consistency

across clinical trial sites. During soundfield measures, the contralateral ear should be plugged or masked, as needed, taking special consideration for unilateral conductive or mixed hearing losses.

If a subject qualifies for bilateral BONEBRIDGE implantation, each ear will be treated separately.

Baseline testing will include the following outcome measures:

- Unaided audiogram, insert earphones (if patent ear canal)
  - Pure-tone air conduction thresholds (250 8000 Hz)
  - Pure-tone bone conduction thresholds (500 4000 Hz)
- Unaided speech testing in noise, soundfield
  - AzBio Sentences in noise at 60 dB SPL with an SNR of +5 dB
  - Speech and noise will be presented at 0° azimuth
  - o One list of 20 sentences will be presented to the individual implant ear(s) alone
  - Lists will be randomized at each clinical trial site
  - o Contralateral ear plugged or masked, as needed
- Unaided speech testing in quiet, soundfield
  - CNC Words in quiet at 60 dB SPL
  - o One list of 50 words will be presented to the individual implant ear(s) alone
  - o Lists will be randomized at each clinical trial site
  - o Contralateral ear plugged or masked, as needed
- Unaided audiogram, soundfield
  - o Soundfield thresholds (500 4000 Hz) in the individual implant ear(s) alone
  - Contralateral ear plugged or masked, as needed
- Unaided signal-to-noise ratio testing, soundfield
  - QuickSIN at 60 dB SPL in the individual implant ear(s) alone
  - Speech and noise will be presented at 0° azimuth
  - Lists will be randomized at each clinical trial site
  - Reported as a signal-to-noise ratio loss
  - o Contralateral ear plugged or masked, as needed
- Subjective questionnaires
  - SSQ12 & HDSS

## 7.2.2 SURGERY

Surgery will be completed within four months of the above pre-operative testing. If surgery is not completed within four months of baseline testing, the testing should be repeated to ensure accuracy. The surgical steps to be followed are drawn from the MED-EL BONEBRIDGE Surgical Guide. These same steps are also detailed in *Appendix A*.

## 7.2.3 DEVICE ACTIVATION

Device activation will occur two to four weeks after surgery. Prior to fitting the device, the following testing should be completed:

- Unaided audiogram, insert earphones (if patent ear canal)
  - o Pure-tone air conduction thresholds (250 8000 Hz)
  - o Pure-tone bone conduction thresholds (500 4000 Hz)

Investigators should fit the SAMBA Audio Processor in accordance with the instructions in the IFU for SYMFIT software.

